### 2.5.2. Secondary exploratory outcomes

The secondary outcomes of this study include assessing the impact of interventions implemented through Telemedicine compared with a control group in the following outcomes:

At the unit level:

- Classification of the unit according to the profiles defined by the SRU and the SMR. The SRU reflects the observed / expected rate of resources used (estimated as ICU length of stay for surviving patients), adjusted by the patient's severity of illness (SAPS 3).

The SMR reflects the observed / expected rate (according to severity score) of hospital deaths. The profiles are a combination of SMR (above or below median) and SRU (above or below median): Each unit can be assigned to one of the four groups:

"most efficient" (SMR and SRU < median); "least efficient" (SMR, SRU > median);

"overachieving" (low SMR, high SRU), "underachieving" (high SMR, low SRU).

At an individual level:

- In-hospital mortality, defined as death by any cause, within the period from the date of ICU admission to the date of hospital discharge or death, whichever comes first.
- Incidence of central line-associated bloodstream infection (CLABSI), as defined by the CDC.
- Incidence of ventilator-associated event (VAE), as defined by the CDC.
- Incidence of catheter-associated urinary tract infection (CAUTI), as defined by the CDC.
- Ventilator-free days at 28 days, defined as the number of days from successfully weaning to day 28; patients who died before weaning were deemed to have no ventilator-free days
- Rate of patients receiving oral or enteral feeding, defined as any amount of oral or enteral diet, during ICU stay
- Rate of patients under light sedation or alert and calm [Richmond Agitation-Sedation Scale (RASS) = -3 to +1]
- Rate of patients under normoxemia [peripheral oxygen saturation (SpO2) between 92% and 96%]

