**Figure 1. Time periods of 30 units in the TELESCOPE trial.**

Randomization	Number of Units	2019								2020				...	2021
		Jun	Jul	Aug	Sept	Oct	Nov	Dec	Jan	Fev	Mar	...	April		
First	14	Baseline	Baseline	Intervention / Control	End enrollment*										
Second	2	Waiting IRB	Baseline	Baseline	Interstitial	Intervention / Control	End enrollment*								
	5	Waiting IRB	Waiting IRB	Baseline	Baseline	Intervention / Control	End enrollment*								
Third	2	Waiting IRB	Waiting IRB	Waiting IRB	Baseline	Baseline	Interstitial	Interstitial	Intervention / Control	End enrollment*					
	4	Waiting IRB	Waiting IRB	Waiting IRB	Waiting IRB	Baseline	Baseline	Interstitial	Intervention / Control	End enrollment*					
	3	Waiting IRB	Waiting IRB	Waiting IRB	Waiting IRB	Waiting IRB	Baseline	Baseline	Intervention / Control	End enrollment*					

\* From April the data collection will continue until hospital outcome or 90-days post ICU admission. The intervention will be maintained in the whole unit until the last included patient is discharged from the ICU.

Interstitial was the period when the ICUs completed their baseline period of two months and were waiting for more blocks to complete their 2-month period to be randomized as a block.

The intervention is open due to the nature of the study (Tele-ICU rounds, quality improvement meetings and delivery of evidence-based clinical protocols). The steering and scientific committees are blinded to the DMRs and monthly feedback/audit meetings.

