### 2.5.3. Other exploratory outcomes

Other outcomes, considered merely exploratory, will be observed:

- ICU mortality

- 24-hour ICU readmission rate
- Proportion of mechanical ventilation (MV) use
- Early reintubation rate (<48h after extubation)
- Accidental extubation rate
- Rate of patients with head of bed elevation for patient under MV
- Rate of central venous catheter (CVC) use and duration
- Rate of urinary catheter use and duration
- Rate of adequate prevention of venous thromboembolism (VTE)
- Rate of patients with adequate glycemic control

The follow-up time to define all outcomes will be truncated at 90 days from ICU admission.

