### 3. Data collection and management

A detailed description of data collection and management is described in the protocol paper. Data collection procedures will be identical in the ICUs assigned to control and to intervention arms, following 1) At ICU admission, including date and hour of admission,

demographic variables, SAPS 3 and SOFA score, reason for admission, comorbidities, functional status, organ support, among others; 2) Data regarding data to ascertain secondary and tertiary outcomes will be collected daily, including documented treatment goals from the DMR; 3) Upon ICU discharge, data on date and time of ICU discharge, place of discharge, and outcome; 4) And finally, at hospital discharge, date and time and outcome.

Trained health care workers collected data, without any involvement of the study committees and investigators. We developed standard CRFs for the trial, with extensive validation and piloting aiming to achieve clarity and consistency. Data was imputed using electronic CRFs in the Research Electronic Data Capture system (REDCap®, USA) via Internet and hosted on a server at the Hospital Israelita Albert Einstein/São Paulo - Brazil.

Data from the intervention arm regarding adherence to the intervention was collected. The main indicators for adherence to the intervention were defined as:

- a. DMR rate per site/bed/day and DMR duration (including individual and periodic feedback to each tele-intensivist).
- b. Rate of recommendations made and validated (accepted and not accepted)/DMR.
- c. Monthly meeting on performance indicators reports: tele-intensivists will send monthly reports to study team, including the executive summary (file sent to the leaderships of each study center/intervention arm, before the monthly meeting) and the meeting record file (structured data about highlighted indicators, action plan, responsibility, and due dates).
- d. Access to the clinical protocols: absolute number of accesses to the video-protocols will be provided and followed.

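### Ventilator-free days are zeroed only for death before weaning, so patients who wean and then die before day 28 are credited with days after death

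*SAP*

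**What the plan says.** Section 2.5.2 fixes the outcome in one sentence with two parts: "defined as the number of days from successfully weaning to day 28; patients who died before weaning were deemed to have no ventilator-free days". The first part is the counting rule and the second is the rule for deaths. Neither part mentions death between weaning and day 28.

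The same section lists in-hospital mortality as a separate outcome: "death by any cause, within the period from the date of ICU admission to the date of hospital discharge or death, whichever comes first". The footnote to Figure 1 says that "data collection will continue until hospital outcome or 90-days post ICU admission", and section 3 lists as the last item collected: "And finally, at hospital discharge, date and time and outcome". In-hospital deaths after weaning will therefore be on file with a date.

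The other sections that could bear on this outcome do not deal with death after weaning:

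- Section 2.5.3 cuts follow-up for all outcomes at 90 days.
- Section 4.2.3.2 handles death as a competing event, but only for ICU length of stay.
- Section 4.2.5 assigns patient-level secondary outcomes to generalized linear mixed models, with no provision specific to this one.

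**The concern.** Ventilator-free days are meant to combine survival with time off the ventilator. The SAP accepts that death should be penalised, since it gives 0 to a patient who dies while still ventilated. It then applies the penalty only according to the order of two events. A patient who dies shortly after weaning gets the same score as one who weans on the same day and survives, and much of that score is made up of days on which the patient was dead.

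This matters for the comparison if the intervention changes the order of weaning and death. An arm in which some patients are weaned earlier but still die would appear to gain ventilator-free days, with no change in mortality and little real time off the ventilator. The table shell in section 5.1.4 provides for an adjusted estimate, confidence interval and p-value for each secondary outcome, so any such artefact would be reported as a treatment effect.

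**Working it through.** The SAP gives no expected value, sample size or power for this outcome, so there is no figure to reproduce. The check applies the definition literally.

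**Notation.** W is the day of weaning and D the day of death, on the same clock as day 28, with W < D < 28.

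- Score under section 2.5.2: 28 − W
- Days alive and off the ventilator, assuming no return to ventilation: D − W
- Days credited after death: 28 − D

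**Single patients** (days are illustrative, not from the SAP)

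| Patient | Score as written | Alive off ventilator | After death |
|---|---|---|---|
| Weaned day 5, died day 8 | 28 − 5 = 23 | 8 − 5 = 3 | 28 − 8 = 20 |
| Weaned day 5, died day 10 | 28 − 5 = 23 | 10 − 5 = 5 | 28 − 10 = 18 |
| Weaned day 7, died day 20 | 28 − 7 = 21 | 20 − 7 = 13 | 28 − 20 = 8 |
| Weaned day 5, alive at day 28 | 28 − 5 = 23 | 23 | 0 |
| Died day 8, never weaned | 0 | 0 | 0 |

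**Does the word successfully exclude these patients?** The SAP does not define it. The only window around extubation is in section 2.5.3: "Early reintubation rate (<48h after extubation". If a 48-hour window were borrowed, the first patient would still count as weaned, being alive 3 days later. Only a requirement of survival to day 28 would remove the problem, and no such requirement is stated. If it were implied, the separate rule for death before weaning would be largely redundant.

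**Shift in an arm mean.** Assume that a share p of ventilated patients, 5% to 15%, wean on day 7 and then die before day 28.

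| Day of death | Post-death days each | p = 5% | p = 15% |
|---|---|---|---|
| 10 | 28 − 10 = 18 | 0.05 × 18 = 0.90 | 0.15 × 18 = 2.70 |
| 14 | 28 − 14 = 14 | 0.05 × 14 = 0.70 | 0.15 × 14 = 2.10 |
| 21 | 28 − 21 = 7 | 0.05 × 7 = 0.35 | 0.15 × 7 = 1.05 |

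Against a score of 0 for these deaths, the excess per patient is 28 − 7 = 21 days. The arm mean is then higher by 0.05 × 21 = 1.05 to 0.15 × 21 = 3.15 days. These are shifts in level and cancel between arms with the same pattern of deaths.

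**Shift in the arm difference.** Assume that in one arm 2 to 5 percentage points of patients die on day 14 after weaning on day 7, rather than dying before weaning. Mortality is unchanged.

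- Total movement: 0.02 × 21 = 0.42 to 0.05 × 21 = 1.05 days
- Of which after death: 0.02 × 14 = 0.28 to 0.05 × 14 = 0.70 days
- Of which alive off the ventilator: 0.02 × 7 = 0.14 to 0.05 × 7 = 0.35 days

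If every in-hospital death by day 28 scored 0, these patients would score 0 in both arms and the movement would be 0.

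**The case against.** The literal reading is hard to dispute. The case on the other side concerns weight and remedy.

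- **Weight.** This is one outcome in a list that section 2.5.2 labels exploratory, and section 4.1.4 says the same of secondary outcomes. Section 4.2.3.2 says no major effect on mortality was expected, and mortality is analysed separately. This stands as a limit on importance. It does not remove the problem: in the scenario above mortality is equal in the two arms and only the order of weaning and death changes. A separate mortality analysis does not correct the score.
- **Size.** Every day and percentage is assumed, and the larger figures are shifts in level, not in treatment effect. This stands. The relevant range is the 0.42–1.05 days for the arm difference, part of which is real time off the ventilator.
- **Remedy.** Stopping the count at death would also remove post-death days, and it would keep the 3 real days of the patient who died on day 8. Scoring 0 for death by day 28 also leaves a jump: with weaning on day 5, death on day 27 scores 0 and death on day 29 scores 23. Both statements are true. Such a jump is inherent in a composite of this kind, so jumps as such are no argument for either rule. The reason to prefer 0 is consistency, because the SAP already scores death as 0 when it precedes weaning.
- **Missing detail.** A time window for successful weaning may sit in the protocol, which is not at hand. This is accepted, and its absence is not part of the finding. The rule for deaths is different: the SAP writes one out, and it is incomplete as written.

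**Conclusion.** The definition is wrong as written. It credits 28 − D days after death to every patient who weans and then dies on day D before day 28, and nothing else in the SAP corrects it.

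On the stated assumptions, the inflation of an arm mean from post-death days runs from 0.35 to 2.70 days across deaths on days 10 to 21. The treatment comparison is distorted only if the share or timing of deaths after weaning differs between arms; a difference of 2–5 percentage points would move it by 0.42–1.05 days. The true size cannot be derived from the SAP.

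The consequence is confined to one exploratory secondary outcome. The primary outcome and the power calculation are unaffected. The definition should be corrected, and section 1 says no analysis had yet been done, so this can be settled before results are seen.

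**What to change.** Amend the definition in section 2.5.2:

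1. Score 0 for any recorded in-hospital death on or before day 28, whether before or after weaning, using the hospital outcome and date already collected.
2. State that patients discharged alive from hospital before day 28 are treated as alive to day 28, because later deaths are not captured.

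While the sentence is open, it would help to state the time off the ventilator that counts as successful weaning, or to point to where the protocol defines it. The correction does not depend on this.

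The cost is one derivation rule and a short change of wording, with no new data. Mean ventilator-free days will be lower in any arm where such deaths occur. Deaths after hospital discharge but before day 28 remain unseen and should be reported as a limitation.

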### 2.5.3. Other exploratory outcomes

Other outcomes, considered merely exploratory, will be observed:

- ICU mortality

- 24-hour ICU readmission rate
- Proportion of mechanical ventilation (MV) use
- Early reintubation rate (<48h after extubation)
- Accidental extubation rate
- Rate of patients with head of bed elevation for patient under MV
- Rate of central venous catheter (CVC) use and duration
- Rate of urinary catheter use and duration
- Rate of adequate prevention of venous thromboembolism (VTE)
- Rate of patients with adequate glycemic control

The follow-up time to define all outcomes will be truncated at 90 days from ICU admission.

## 2.6. Power calculation

### 2.6.1. Original power calculation

Prior to the start of the trial and baseline period, for the funding application, we estimated a mean ICU length-of-stay of 8 [standard deviation (SD) 10] days for general adult public ICUs in Brazil. We used data from published literature and reports from the online project “UTIs Brasileiras”. In 2018, the “UTIs Brasileiras” dashboard had data of ICU LOS from 242 public ICUs in Brazil (n=3,199 beds). Using data from 20 ICUs (10 ICUs from [name] et al, 10 ICUs from the ORCHESTRA study, available in the *ems* R package), we estimated an intraclass correlation coefficient (ICC) of 0.018. Considering a two-arm cluster trial with an ICC of 0.018, for a minimum difference of an average length of stay of 1.5 days (8.0 to 6.5 days)

and SD of 10 days, power 80%, alpha 5%, we would need a total of 30 clusters (15 intervention units and 15 control units) with an average cluster size of 500 patients per ICU over a period of 18 months. Cluster size can vary and if the cluster size variation is high, usually measured by the coefficient of variation (CV), the power of the trial decreases. We estimated the CV using the expected minimum and maximum method of the cluster size: assuming a minimum cluster size of 350 patients and maximum of 650 patients (i.e., range 300, approximated SD of 75), for a mean size of 500 patients, we would have an approximated CV of 0.15 and maintain 80% power.

#### 2.6.2. Power after baseline period

We had pre-specified in the original protocol that once the baseline period was completed, we could review the power calculation. We evaluated the baseline period and the mean ICU LOS was 7.8 days, SD 9.8 and an ICC of 0.087 for a model without covariate adjustment. We had an ICU LOS mean and SD very close to the original power calculation (mean 8 and SD 10), but higher ICC than predicted. The original power estimation did not account for the use of the data from the baseline period in the model for the primary outcome, because it was not certain we would have funding to collect individual-level data for the selected ICUs to characterize the baseline period. However, we specified in the original protocol that once the baseline period was established, we would adjust the model for the primary outcome accounting for the baseline period and re-estimating the power of the trial. Therefore, using the framework suggested by Hemming et al, we re-estimated the power accounting for the baseline period in September 2019. This method uses the cluster auto-correlation (CAC), defined by the ratio of the between-period ICC to the within-

period ICC. Considering a cluster parallel trial with baseline measure, with cross-sectional sampling structure, a correlation structure of a two-period decay, a coefficient of variation of clusters size of 0.4 (taken from the baseline period), we would maintain 80% power until a CAC value of  $\geq 0.906$ , without considering covariate-adjustment. We estimated the CAC on the 20 ICUs used for the estimation of initial ICC, using follow-up periods similar to the TELESCOPE trial, and in all occasions it was higher than 0.960. Considering the dynamic of ICU LOS and its high correlation overtime, we expect CAC to be high. Two issues that could reduce the power must be taken into account: 1) this new power calculation assumes that ICUs would have the same number of patients recruited in the baseline and post-randomization period (n=500); 2) equal number of ICUs randomized to intervention and control at each block, which occurred in the first block, but not for the second and third block. However, these estimations did not account for the covariate adjustment in the main model, also pre-specified in the original protocol, which decrease the ICC and increase precision by reducing the between-center variance and that we will adjust for randomization block in the analysis. Based on this scenario, after a meeting with an external advisory board on 05/10/2020, the steering committee decided to keep the original sample size and power calculation, conditioning it to updating the analysis plan in order to keep the covariate adjustment and to account for the baseline period.

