arms. We applied the same random sorting of order and potential unit allocations. The meaning of 0 and 1 was kept the same as the first block randomization (i.e., 0 to intervention and 1 to control) because it must follow the first block ascertainment. To ensure allocation concealment, all units were enrolled prior to randomization and the Ethics approval and the ICU and hospital coordinators signed the agreement with commitment to the trial; the statistician responsible for the randomization list received only the ICU identifier code, unaware of which unit it referred to; the allocation list was sent to the study coordinator, who informed simultaneously the ICUs about the randomization and allocation.

The allocations were done after the completion of the baseline, on 05 August 2019, 16 October 2019, and 29 January 2020, using the software R (v. 3.5.2).

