## 4. Statistical methods analysis

### 4.1. General analysis issues

#### 4.1.1. Analysis population

Primary statistical analyses will be performed according to the intention-to-treat principle. Patient outcomes will be analyzed according to the randomization of the ICU each patient was in, regardless of whether or not the intervention was applied in that ICU. The baseline period is defined as the first two months of data collection in each ICU. The period for the evaluation of the intervention will be defined as the day after the randomization, thus patients admitted to the ICUs the next day of randomization are accounted as of the intervention/control period. Primary statistical analysis will also consider the baseline period in the analyses, while patients admitted to some of the ICUs during the “Interstitial” period (between baseline and randomization) will be excluded.

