##### 4.2.1. Analysis of the primary outcome

The linear mixed model for the primary outcome will be the following:

$$Y_{ijk} = \beta_0 + \beta_1 X_{ij} + \beta_2 j + \beta_3 Z_{ijk} + \beta_4 L_{ij} + \mu_i + \nu_{ij} + \epsilon_{ijk} \quad \text{Equation (1)}$$

for cluster  $i$ , time-period  $j$  and participant  $k$ , where  $X_i$  denotes the trial arm for cluster  $i$  (coded 0 or 1), and  $j$  denotes the time-period in which participant  $k$  in cluster  $i$  is assessed (0 for baseline, 1 for after randomization). The individual error term is assumed to be Normally distributed and independent of  $\nu_{ij}$  and  $\mu_i$ . Random terms are assumed to be Normally distributed, and  $\nu_{ij}$  is assumed independent of  $\mu_i$ .  $Z_{ijk}$  and  $L_{ij}$  are the matrix of covariates at the individual level and unit level, respectively.  $\beta_1$  is the coefficient of interest for the trial, i.e., the estimate for the difference between those receiving the intervention and those in the control group.

For the primary outcome, we will include the index admission of a patient, i.e., we will not include ICU readmissions. The primary outcome – ICU LOS – will be log-transformed to account for the normality of the residuals of the linear mixed model. These two steps (not including readmissions and log-transformation) were used for the power calculations.

We will use the identity link in the model for the primary outcome and the Satterthwaite's degree-of-freedom correction.

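### The stated 80% power down to a CAC of 0.906 needs 500 baseline patients per ICU; a two-month baseline supplies about 56, which on the day scale needs a CAC of about 0.96 to 0.97

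*SAP*

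**What the plan says.** Section 2.6.1 plans 15 ICUs per arm "with an average cluster size of 500 patients per ICU over a period of 18 months", to detect 1.5 days with an SD of 10 days and an ICC of 0.018.

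Section 2.6.2 reports a much higher baseline ICC, 0.087, and re-estimates power using the baseline data. With a cluster-size CV of 0.4 and no covariates, "we would maintain 80% power until a CAC value of" at least 0.906. In 20 external ICUs the CAC was estimated and "in all occasions it was higher than 0.960".

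The section then lists two issues that might lower power. The first is that "this new power calculation assumes that ICUs would have the same number of patients recruited in the baseline and post-randomization period (n=500"). It gives neither an expected baseline size nor the loss of power. It answers the issue by pointing to covariate adjustment and reports that, after an external advisory meeting dated 05/10/2020, "the steering committee decided to keep the original sample size and power calculation", on condition that the analysis adjusts for covariates and uses the baseline.

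On the baseline itself, section 4.1.1 says: "The baseline period is defined as the first two months of data collection in each ICU". Section 2.4 adds: "The allocations were done after the completion of the baseline, on 05 August 2019, 16 October 2019, and 29 January 2020". On the scale of the calculation, section 4.2.1 says: "These two steps (not including readmissions and log-transformation) were used for the power calculations".

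**The concern.** The power case now depends on the baseline data. With an ICC of 0.087 and no baseline, power would be only about 25% (shown in the working). How far the baseline helps depends on the CAC and on how precisely each ICU's baseline mean is estimated, that is, on the number of baseline patients.

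The 0.906 threshold assumes about nine times the baseline data that two months can supply at the planned rate. A reader who sets a required 0.906 against external values above 0.960 sees ample room, and the decision to keep the sample size was taken on that scenario. The shortfall is not merely possible: a two-month baseline cannot match an 18-month follow-up at a steady admission rate. All baselines were complete by 29 January 2020, before the 05/10/2020 meeting on either reading of that date, so actual counts were available.

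**Working it through.** **Inputs.** Difference 1.5 days, SD 10, 15 ICUs per arm, 500 patients per ICU in 18 months (section 2.6.1). ICC 0.087 and CV 0.4 (section 2.6.2). Two-sided alpha of 5% (sidedness assumed). Baseline of two months (section 4.1.1), so m0 = 500/18 × 2 = 55.6 patients per ICU.

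Follow-up by randomization block, from the allocation dates and Figure 1 to the end of March or April 2021, is 19.8–20.8, 17.5–18.5 and 14.0–15.0 months. Then 500 × 2/months gives 48–50, 54–57 and 67–71 baseline patients.

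**Formula.** Two periods, cross-sectional sampling, no arm difference at baseline (as in Equation 1), m1 = 500:

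Var(β1) = (2 × SD²/15) × (b − c²/a)

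- r = ICC × (1 + CV²) = 0.087 × 1.16 = 0.10092
- a = r + (1 − ICC)/m0
- b = r + (1 − ICC)/500 = 0.10092 + 0.00183 = 0.10275
- c = CAC × r

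Power (normal test) = Φ(1.5/SE − 1.96).

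**The plan's figure, 500/500.** Here a = b = 0.10275. At CAC 0.906, c = 0.09143 and Var = 13.333 × (0.10275 − 0.08137) = 0.285. SE = 0.534, 1.5/SE = 2.81, power 80.2%. The 80% threshold is 0.905, so the SAP's 0.906 is reproduced on the day scale.

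**The same with 55.6 baseline patients.** Now a = 0.10092 + 0.01643 = 0.11735.

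- CAC 0.906: Var = 13.333 × (0.10275 − 0.07124) = 0.420, SE = 0.648, 1.5/SE = 2.31, power about 64%.
- CAC 0.96: c = 0.09688, Var = 13.333 × (0.10275 − 0.07998) = 0.304, SE = 0.551, 1.5/SE = 2.72, power 77.7%.

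A second method, generalized least squares (GLS) with gamma-distributed ICU sizes at CV 0.4, gives the other end of each range:

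| Baseline/follow-up | CAC for 80% | Power at 0.906 | Power at 0.96 |
|---|---|---|---|
| 500/500 | 0.892–0.905 | 80–84% | 97–98% |
| 56/500 | 0.963–0.967 | 64–67% | 78–79% |
| 45 to 71/500 | 0.947–0.983 | not tabulated | 73–84% |

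At 56/500, power is 81–82% at CAC 0.97 and 84–85% at 0.98. With a t test on 28 df the 56/500 threshold rises to 0.972–0.976 and power falls by about 3 points. With SD 9.8 instead of 10, the GLS form and a normal test, it is 0.956.

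**Baseline needed for 80%.** At CAC 0.906, 205–462 patients, or 7–17 months at the planned rate. At CAC 0.96, 58–63 patients.

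**No baseline.** Var = 13.333 × 0.10275 = 1.370, SE = 1.170, 1.5/SE = 1.28, power about 25%.

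**Covariates.** 80% power needs Var = (1.5/2.80)² = 0.287. From 0.304 (CAC 0.96) that is a cut of 5.5%; from 0.420 (CAC 0.906), 32%. Across both methods the cuts in all variance components are 2–6% and 27–32%.

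**Log scale.** Assume lognormal stays with mean 8 and SD 10, a ratio of 6.5/8 and an unchanged ICC of 0.087. Then SD = √ln(1 + (10/8)²) = 0.970 and the effect is ln(8/6.5) = 0.208. The 500/500 threshold would be 0.73–0.77, not 0.906, and power with 56 baseline patients at CAC 0.906 would be 91–93%. With an assumed log-scale ICC of 0.15 it would be 79–82%.

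**The case against.** The SAP does disclose the equal-size assumption as a threat to power, in the same paragraph as the figure. That stands: 0.906 is not an arithmetic error, and what is missing is the size of the loss.

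The 56 is a planning figure and may be low. At a mean stay of 7.8 days, 56 patients in about 61 days would fill 8 beds, the eligibility minimum, to 56 × 7.8/(8 × 61) = 90%. If the trial ICUs had the 13.2 beds of the public ICUs cited for planning (3,199/242) and 70–100% occupancy, two months would yield about 72–103 patients. With 103 the threshold is 0.928–0.944. This is a fair reason to use actual counts. But those bed numbers and occupancies are not given for the trial ICUs, and every such scenario still lies above 0.906.

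At the external floor of 0.96 the shortfall is small, and a 2–6% cut in variance would close it. With adjustment for SAPS 3, ventilation, admission type and ICU-level covariates that is plausible, but the SAP gives no adjusted ICC or variance to show it.

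The scale could reverse the conclusion, since section 4.2.1 says the power calculations were log-transformed. Against that, only day-scale inputs are given, and those reproduce 0.906. The ambiguity itself needs resolving.

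Recruitment is complete, so neither the sample size nor the test will change. That limits the consequence, but the power statement remains wrong for this design.

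**Conclusion.** The concern holds. The threshold of 0.906 is correct for 500 patients per ICU in both periods, but the two-month baseline does not supply them. On the SAP's own rate and day-scale inputs, unadjusted, the required CAC is about 0.96 to 0.97. Power is 64–67% at 0.906 and 78–79% at 0.96, against 80–84% and 97–98% under 500/500. The apparent margin over the external CAC values becomes small or uncertain.

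This does not show that the trial is underpowered. The size rests on a derived 56 baseline patients (48–71 by block), no covariate gain and the day scale. A larger baseline, covariate adjustment or a log-scale calculation would each help, and the scale matters as much as the baseline size.

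**What to change.** In section 2.6.2:

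- Keep 0.906, labelled as valid only for 500 patients per ICU in each period.
- Beside it, report the CAC threshold and power from the actual baseline and follow-up counts per ICU, using the method for unequal baseline and endline sizes already cited as reference 31. Until those are given, the planning-figure result (day scale, unadjusted) is a threshold of about 0.96–0.97, with power of 78–79% at 0.96 and 64–67% at 0.906.
- State whether the calculation is in days or log days, with the SD, ICC and effect on that scale, and reconcile this with section 4.2.1.
- Quantify the expected gain from patient- and ICU-level covariates, or say that it is unquantified.

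The cost is a change of wording and one recomputation from data already held. No patients are added, and the model and primary test stay as they are. On the day scale the stated power becomes less favourable.
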